IWRS	Interactive Web Randomization System
kDa	kilodalton

Abbreviation	Definition
LD	low dose
MedDRA	Medical Dictionary for Regulatory Activities
MMRM	mixed model repeated measures
OLS	open-label, long-term, safety (Study Protocol 1720304)
Onabot	onabotulinumtoxinA
PGIC	Patient Global Impression of Change
PI	principal investigator
PP	per protocol
PT	prothrombin time
QOL	quality of life
QT	measure of time between start of the q wave and the end of the t wave in the heart's electrical conduction
QTcF	corrected QT interval using Fridericia's correction formula
REB	Research Ethics Board
Revance	Revance Therapeutics, Inc.
RT002	previous company name for drug product daxibotulinumtoxinA for injection
RTP004	Revance novel excipient
RTT150	previous company name for drug substance, daxibotulinumtoxinA
SAE	serious adverse event
SF-36	Short Form-36 Survey
SOA	Schedule of Activities
SOP	standard operating procedure
SUSAR	suspected unexpected serious adverse reaction
TdP	Torsade de Pointe
TEAE	treatment-emergent adverse event
TSQ	Treatment Satisfaction Questionnaire
TWSTRS	Toronto Western Spasmodic Torticollis Rating Scale
U	units (botulinum toxin)
UP	unanticipated problem
US	United States
WOCBP	women of child bearing potential
WPAI	Work Productivity and Activity Impairment

STATEMENT OF COMPLIANCE

The trial will be conducted in accordance with the protocol, International Council for Harmonisation Good Clinical Practice (ICH GCP), all applicable Food and Drug Administration (FDA), European Medicines Agency (EMA), Health Canada, and national regulations. The principal investigator (PI) will assure that no deviation from, or changes to the protocol will take place without prior agreement from the Investigational New Drug (IND) sponsor, funding agency and documented approval from the Institutional Review Board (IRB)/Research Ethics Board (REB)/ Ethics Committee (EC), except where necessary to eliminate an immediate hazard(s) to the trial participants. All personnel involved in the conduct of this study have completed Human Subjects Protection and ICH GCP Training.

The protocol, informed consent form(s), recruitment materials, and all participant materials will be submitted to the Institutional Review Board (IRB)/Research Ethics Board (REB)/ Ethics Committee (EC) for review and approval. Approval of both the protocol and the informed consent form must be obtained before any participant is enrolled. Any amendments to the protocol, informed consent form(s), recruitment materials, and all participant materials will require review and approval by the IRB/REB/EC before the changes are implemented to the study. All changes to the informed consent form will be IRB/REB/EC approved prior to implementation; a determination will be made regarding whether a new informed consent needs to be obtained from participants who provided informed consent, using a previously approved informed consent form (ICF).

1 PROTOCOL SUMMARY

1.1 SYNOPSIS

Title: **A Phase 3, Open-Label, Multi-Center Trial to Evaluate the Long-Term Safety and Efficacy of Repeat Treatments of DaxibotulinumtoxinA for Injection in Adults with Isolated Cervical Dystonia (ASPEN-OLS)**

Study Description: This is a Phase 3, open-label, multi-center trial to evaluate the long-term safety, efficacy, and immunogenicity of up to four continuous treatment cycles of daxibotulinumtoxinA (DAXI) for injection at doses of 125 U, 200 U, 250 U, and 300 U in adults with isolated cervical dystonia (CD).

Approximately 350 adult subjects will be recruited from study centers in the United States, Canada, and Europe who were enrolled in Study Protocol 1720302. These subjects from Study 1720302 include:

- Those with no reduction or increase from baseline in the average TWSTRS-total score at Weeks 4 and 6 (i.e., no improvement or worsened disease), and the investigator agreed that there was a need for retreatment based on the subject's symptoms and neurologic exam findings
- Those who benefited from study treatment and completed follow-up study visits up to the time point of when their TWSTRS-total score reached/exceeded their target TWSTRS
- Those who benefited from study treatment but subsequently experienced significant recurrence of CD symptoms (e.g. pain) during the study before their TWSTRS-total score reached their target TWSTRS score and requested retreatment, which the investigator determined was warranted based on the subject's symptoms and neurologic exam findings
- Those who completed study visits up to Week 36 and their TWSTRS-total score never reached their target TWSTRS score. The investigator determined that these subjects can be followed in the OLS until their TWSTRS-total score is the same or higher than their target TWSTRS score or until they request retreatment, which the investigator determined was clinically indicated

All subjects will have up to 7 days from their End-of-Study (EOS) Visit in Study Protocol 1720302 to decide if they want to enroll in this study. After the 7-day decision-making period, any subjects who have not made an enrollment decision will be considered "not interested in the OLS."

After a subject has decided to enroll in the OLS, s/he will have up to 21 days to complete the screening procedures and enroll in the OLS. After 21 days, subjects who have NOT completed the screening procedures will be considered a screen failure. To be reconsidered for enrollment to the OLS, the subject will be required to repeat all screening procedures to reconfirm eligibility for enrollment in the OLS. These criteria also apply to subjects who missed the 7-day decision-making window to enroll in the OLS.

A written informed consent must be obtained from all subjects participating in the OLS before any trial-related procedures (including any screening procedures) are performed.

Eligible subjects who completed participation in Study Protocol 1720302 may be eligible for the first treatment (Baseline Treatment in Treatment Cycle 1 of OLS) during their EOS Visit window, but treatment may not be administered on the same day as the EOS Visit due to unavailability of screening safety laboratory results. In this case, the EOS Visit procedures and laboratory results from Study Protocol 1720302 will serve as the baseline data for this trial.

This study will also recruit new BoNT treatment-naïve or -experienced adult subjects, who were not enrolled in Study Protocol 1720302.

[REDACTED]

[REDACTED]

[REDACTED]

- [REDACTED]

- [REDACTED]

[REDACTED]

- [REDACTED]

- [REDACTED]

[REDACTED]

[REDACTED]

[REDACTED]

[REDACTED]

Two weeks after the Baseline/Treatment Study Visit (Day 1), study site staff will call the subject to inquire about CD symptom status and adverse events (AEs). The subject will return for protocol-specified assessments at Weeks 4, 6, 12, and every 4 weeks thereafter, up to Week 52 or EOS Visit.

Primary endpoints are safety and immunogenicity after multiple continuous treatment cycles of DAXI for injection. [REDACTED]

[REDACTED]

[REDACTED]

[REDACTED]

[REDACTED]

[REDACTED]

[REDACTED]

A subject may not be re-enrolled in the OLS after the EOS Visit (or after early discontinuation).

Study Visits and Telephone Calls:

- Screening (Days -21 to -1)
- Treatment #1, #2, #3, and #4
- Follow-up telephone calls after each Treatment:
 - Week 2 after each treatment (study site staff will call the subject)
- Follow-up visits after each Treatment:
 - Follow-up visits at Weeks 4, 6, 12, and every 4 weeks thereafter until the EOS Visit (52 weeks after Treatment #1 [Study Baseline]) (See Figure 1 Figure 1 and Table 1).

Safety Evaluations:

- Laboratory tests (hematology, prothrombin time [PT], chemistry, and urinalysis)

[REDACTED]

[REDACTED]

- Physical and neurological examinations
- Columbia-Suicide Severity Rating Scale (C-SSRS)
- Dysphagia Severity Scale
- Vital signs
- Spirometry: the forced expiratory volume in the first second of exhalation (FEV₁) and forced vital capacity (FVC)
- 12-lead electrocardiograms (ECGs)
- Injection site evaluations
- Concomitant medications
- Treatment-emergent adverse events (TEAEs)

[REDACTED]

Efficacy Evaluations:

- Toronto Western Spasmodic Torticollis Rating Scale (TWSTRS)
- Clinical Global Impression of Change (CGIC)
- Patient Global Impression of Change (PGIC)
- Cervical Dystonia Impact Profile (CDIP-58)

- Treatment Satisfaction Questionnaire (TSQ)
- Work Productivity and Activity Impairment (WPAI) Questionnaire
- Short Form-36 (SF-36) Survey

Diagnosis and Main Eligibility Criteria:

Subjects with a diagnosis of isolated CD meeting the full eligibility criteria may participate in the study. Major inclusion/exclusion criteria are presented below.

Major Inclusion Criteria:

- Adults, 18 to 80 years of age
- Meets diagnostic criteria for isolated CD (idiopathic; dystonic symptoms localized to the head, neck, shoulder areas) with at least moderate severity at Baseline (Day 1), defined as a TWSTRS-total score of at least 20, with at least 15 on the TWSTRS-Severity subscale, at least 3 on the TWSTRS-Disability subscale, and at least 1 on the TWSTRS-Pain subscale (minimum TWSTRS subscale criteria applicable only to subjects not previously enrolled in Study Protocol 1720302)
- Subjects who were previously enrolled in Study Protocol 1720302, and completed the study, including:
 - Those with no reduction or have an increase from baseline in the average TWSTRS-total score at Weeks 4 and 6 (i.e., no improvement or worsened disease status), and the investigator agreed that there was a need for retreatment based on the subject's symptoms and neurologic exam findings
 - Those who benefited from study treatment and completed follow-up study visits up to the time point of when their TWSTRS-total score reached/exceeded their target TWSTRS score
 - Those who benefited from study treatment but subsequently experienced significant recurrence of CD symptoms (e.g. pain) during the study before their TWSTRS-total score reached their target TWSTRS score and requested retreatment, which the investigator determined was warranted based on the subject's symptoms and neurologic exam findings
 - Those who completed study visits up to Week 36 and their TWSTRS-total score never reached their target TWSTRS score and they never requested another treatment. The investigator determined that these subjects can be followed in the OLS until their TWSTRS-total score is the same or higher than their target TWSTRS score or until they request retreatment, which the investigator determined is clinically indicated
- De novo subjects (not previously enrolled in Study Protocol 1720302):
 - Naïve to BoNT treatment
 - BoNT treatment-experienced; if previously treated with BoNTA, the subject must have demonstrated a clinically meaningful response to the last BoNTA treatment based on the clinical judgment of the investigator

Major Exclusion Criteria:

- Cervical dystonia attributable to an underlying etiology, (e.g., traumatic torticollis or tardive torticollis)
- Predominant retrocollis or anterocollis CD
- Significant dystonia in other body areas, or is currently being treated with botulinum toxin (BoNT) for dystonia in areas other than those associated with isolated CD
- Severe dysphagia (Grade 3 or 4 on the Dysphagia Severity Scale) at Screening or Baseline (prior to study treatment)

- █ [REDACTED]
- █ [REDACTED]
- █ [REDACTED]

Objectives:

Primary Objectives:

- To evaluate the long-term safety of multiple continuous treatments of DAXI for injection
- To assess immunogenicity to BoNTA and RTP004 after multiple treatments of DAXI for injection

- █ [REDACTED]
- █ [REDACTED]
- █ [REDACTED]
- █ [REDACTED]
- █ [REDACTED]
- █ [REDACTED]
- █ [REDACTED]

symptoms. BoNT treatment-experienced subjects may include those who were previously enrolled in Study Protocol 1720302.

Statistical Methods:

Sample Size Justification:

The sample size for this study is based on a requirement from Regulatory Authorities to collect safety data on approximately 350 subjects treated with DAXI once and long-term safety data on at least 100 adult subjects treated with 3 or 4 continuous treatments of low-dose or high-dose DAXI for injection, with at least 50 subjects treated with the high-dose DAXI for injection for 3 or 4 continuous treatments. [REDACTED]

[REDACTED]

Analysis Populations:

Intent-to-Treat Population:

The intent-to-treat (ITT) population is defined as all subjects who enrolled in the OLS and received at least one dose of study drug.

The ITT population will be analyzed by specific treatment cycle and dose. The ITT analysis set will be used to conduct efficacy analyses.

[REDACTED]

Safety Population:

The safety analysis population consists of all randomized subjects who received at least 1 injection of study drug. Subjects will be grouped by the treatment they receive rather than their treatment assignment. The safety analysis set will be used to conduct safety analyses.

[figure not shown]
Demographic and baseline characteristics will be summarized for the ITT, PP, and safety populations.

[figure not shown]
Phase:
Description of Sites/Facilities
Enrolling Participants:

[figure not shown]
3
Approximately 80 sites in the US, Canada, and Europe will participate in the study.

[Redacted text block containing multiple lines of blacked-out information]

Participant Duration: Up to 55 weeks, including 3 weeks for screening

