9.3 PRIMARY STUDY OBJECTIVES AND ENDPOINTS

Primary Objectives:

- To evaluate the long-term safety of multiple continuous treatments of DAXI for injection
- To assess immunogenicity to BoNTA and RTP004 after multiple treatments of DAXI for injection

Primary Endpoints:

[figure not shown]
- Dose- and cycle-specific incidence of drug-related adverse events
- Dose- and cycle-specific incidence of drug discontinuation due to drug-related AEs
- Dose- and cycle-specific incidence of immunogenicity

[REDACTED]

[REDACTED]

- [REDACTED]
- [REDACTED]
- [REDACTED]

[REDACTED]

- [REDACTED]
- [REDACTED]
- [REDACTED]
- [REDACTED]
- [REDACTED]
- [REDACTED]

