3.4. Brief Description

This is a Phase 3, open-label, multi-center trial to evaluate the long-term safety, efficacy, and immunogenicity of up to four continuous treatment cycles of DAXI for injection at doses of 125 U, 200 U, 250 U, and 300 U in adults with isolated CD at study centers across the United States, Canada, and Europe.

Approximately 350 adult subjects will be recruited from study centers who were previously enrolled in Protocol 1720302 entitled [A Phase 3, Randomized, Double-Blind, Placebo-Controlled, Parallel Group, Multi-Center Trial to Evaluate the Efficacy and Safety of a Single Treatment of DaxibotulinumtoxinA for Injection in Adults with Isolated Cervical Dystonia (ASPEN-1)]. These subjects will have 7 days from their End-of-Study (EOS) Visit in Protocol 1720302 to decide if they want to enroll in this study. After enrolling, subjects will have up to 21 days to complete screening procedures. After 21 days, subjects who have NOT completed the screening procedures will be considered a screen failure. To be reconsidered for enrollment to this study, the subject will be required to repeat all screening procedures to reconfirm eligibility for enrollment. These criteria also apply to subjects who missed the 7-day decision-making window to enroll in this study. This study will also recruit new botulinum neurotoxin (BoNT) treatment-naïve or -experienced adult subjects who were not enrolled in Protocol 1720302.

[REDACTED]

[REDACTED]

This document is confidential.

[REDACTED]

The primary endpoints are safety and immunogenicity. [REDACTED]

[REDACTED]

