4.1. Primary Endpoints

The primary endpoints of this study are:

- The dose- and cycle-specific incidence of drug-related adverse events (AEs)
- The dose- and cycle-specific incidence of study drug discontinuation due to drug-related AEs
- The dose- and cycle-specific incidence of treatment-emergent immunogenicity

This document is confidential.

5. Analysis Sets

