6.2. Key Definitions

Study day will be assigned as follows:

[figure not shown]
- Before the first study medication dose date, study day = visit date – dose date.
- After the first study medication dose date, study day = visit date – dose date + 1.

The day the study medication is first given is Day 1, and the day before the study medication is first given is considered Day -1.

Unless otherwise specified, baseline value is defined as the last non-missing value before the first study medication administration. Change from baseline is defined as the post-baseline value minus the baseline value (post baseline – baseline). Percent change from baseline is defined as 100 times post-baseline value minus baseline value divided by the baseline value ($100 * (\text{post baseline} - \text{baseline}) / \text{baseline}$).

[figure not shown]
[REDACTED]

This document is confidential.

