7.1. Subject Disposition and Withdrawals

The number and percentage of subjects screened, enrolled, completed, and discontinued will be summarized along with the reasons for discontinuation and will be summarized. The number of subjects who received treatment in each cycle will be summarized. The number of subjects in each study analysis population will also be presented. Enrollment will be summarized by Rollover and DeNovo. Listings will be provided for disposition data, study populations and reasons for exclusion from the study population, and inclusion/exclusion criteria not met.

The reason for discontinuation will also be summarized by cycle. A summary of the duration of the subject participation in the study will be produced, including the n, mean, SD, median, minimum, and maximum duration in weeks, as well as the number and percentage of subjects in the following categories of duration: <4 weeks, 4 to <12 weeks, 12 to <24 weeks, and 24 to <36 weeks, and 36 weeks or more. If a subject is lost to follow-up, their participation in the study will be calculated based on their date of last visit. Duration of study participation will also be summarized overall, across all cycles using the following categories: < 24 weeks, 24 to < 36 weeks, 36 to < 48 weeks, and 48 weeks or more.

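### For rollover subjects given DAXI in 1720302, the visible baseline rules put the antibody baseline after a DAXI exposure, so conversions from that injection are missed or assigned to OLS cycle 1

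*Protocol*

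**What the plan says.** The objective in Protocol 9.3 is "To assess immunogenicity to BoNTA and RTP004 after multiple treatments of DAXI for injection". SAP 4.1 gives the matching primary endpoint as "The dose- and cycle-specific incidence of treatment-emergent immunogenicity". Protocol 3 agrees, while Protocol 9.3 lists it as "Dose- and cycle-specific incidence of immunogenicity", without the treatment-emergent qualifier. No visible text defines treatment-emergent for antibodies.

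Two baseline rules are visible:

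- Protocol 1.1 and 4.1: "the EOS Visit procedures and laboratory results from Study Protocol 1720302 will serve as the baseline data for this trial". The sentence is limited to rollovers who may be treated within their 1720302 EOS Visit window.
- SAP 6.2: "Unless otherwise specified, baseline value is defined as the last non-missing value before the first study medication administration". This is a default and leaves room for an exception.

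Protocol 8.2.7 lists serum antibodies among the clinical laboratory samples, so a rule about laboratory results naturally reaches them.

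The title of the parent trial, given in SAP 3.4, describes a randomised, placebo-controlled study to "Evaluate the Efficacy and Safety of a Single Treatment of DaxibotulinumtoxinA for Injection in Adults with Isolated Cervical Dystonia". About 350 subjects are to come from it, and de novo subjects are also recruited.

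The only visible rollover split is in SAP 7.1: "Enrollment will be summarized by Rollover and DeNovo". The only visible link back to the 1720302 injection is in Protocol 9.6, for duration of effect in subjects who rolled over at Week 36.

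**The concern.** A subject randomised to DAXI in 1720302 enters the OLS having already received the toxin and RTP004, which the Protocol's abbreviation list calls the sponsor's novel excipient. If that subject's antibody baseline is the 1720302 EOS sample, or the last sample before the first OLS dose, it cannot separate antibodies raised by the 1720302 injection from antibodies present before any DAXI.

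Three things follow under the visible rules:

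- A conversion already detectable at that sample becomes a baseline positive.
- A conversion from the same injection that becomes detectable only later is credited to OLS cycle 1.
- The cycle label does not count the same thing for everyone. It is the DAXI injection number for de novo and former-placebo subjects, and one less than that number for former-DAXI subjects.

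The objective asks what happens after multiple treatments. A table indexed only by OLS cycle, with no split by earlier DAXI exposure, answers that less directly than the sponsor's own data would allow.

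**Working it through.** The documents state no antibody incidence, and the sample size is a regulatory exposure count, so there is no figure to reproduce. The ordering of events comes from the documents. The sizes below are illustrative.

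**Inputs**

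- N = 350 subjects from 1720302 (Protocol 1.1; SAP 3.4).
- f = share of them given DAXI in 1720302. Not in the documents; assumed 0.50 to 0.75.
- p = conversion probability per DAXI injection. Not in the documents; assumed 0.5% to 2%, extended to 5% as a check.
- g = share of 1720302 conversions that become detectable only after the OLS baseline. Assumed 0, 0.25 or 0.50.

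**Step 1: ordering**

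| Group | DAXI injections before OLS baseline | OLS cycle k is DAXI injection number |
|---|---|---|
| De novo (taken as DAXI-naive) | 0 | k |
| Former placebo | 0 | k |
| Former DAXI | 1 | k + 1 |

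The third row is the same under both visible baseline rules.

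**Step 2: conversions classed as baseline-positive**, N × f × p, if all are detectable at the OLS baseline:

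- Low: 350 × 0.50 × 0.005 = 0.9
- Middle: 350 × 2/3 × 0.01 = 2.3
- High: 350 × 0.75 × 0.02 = 5.25
- Check at p = 5%: 350 × 0.75 × 0.05 = 13.1

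**Step 3: cumulative incidence among rollovers**, with p = 1% and f = 2/3:

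- Since first DAXI: f[1 − (1−p)^(k+1)] + (1−f)[1 − (1−p)^k]
- Counted from the OLS baseline, all subjects in the denominator: f(1−p)[1 − (1−p)^k] + (1−f)[1 − (1−p)^k]

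| OLS cycles | Since first DAXI | From OLS baseline | Relative loss |
|---|---|---|---|
| 1 | 1.66% | 0.99% | 40% |
| 4 | 4.58% | 3.91% | 15% |

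**Step 4: incidence within cycle 1, baseline-negative subjects as denominator, g = 0.** Conversions are f(1−p)p + (1−f)p and subjects at risk are f(1−p) + (1−f). The ratio is p, or 1.00%, so nothing is lost on this measure.

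**Step 5: late detection.** The share of all subjects counted as converting in cycle 1 is (1−f)p + f[pg + (1−p)p]:

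- g = 0.25: 0.0033 + 2/3 × (0.0025 + 0.0099) = 1.16%
- g = 0.50: 0.0033 + 2/3 × (0.0050 + 0.0099) = 1.33%

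Both exceed the 1.00% risk per injection, so cycle 1 is overstated.

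**The case against.** The strongest reply is that the governing rule may exist but be hidden. The SAP contents show a redacted entry between 9.5 and 9.7, text after 6.2 is redacted, and the antibody text in Protocol 8.2.7 ends in a redacted block. The SAP 6.2 default yields to any such rule. A pre-1720302 antibody baseline, or a titre-rise criterion, would remove much of the problem. This stands and limits confidence. A reader might infer that the plan has no antibody baseline rule, but the documents show only that none is visible.

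A reader might also infer that every rollover is affected. That is not so. Former-placebo subjects had no DAXI in 1720302, and the Protocol's EOS sentence covers only those treated in the EOS window. For other former-DAXI subjects the point rests on SAP 6.2.

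A third tempting inference is that the primary endpoint is biased low and flatters the product. The endpoint is worded as incidence by dose and cycle within the OLS, not cumulatively since first DAXI. Steps 4 and 5 show that per-cycle incidence can be unchanged or too high, so no single direction of bias is supported.

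Finally, a fragment left in the Protocol 1.1 objectives notes that BoNT-experienced subjects may include those from 1720302, which hints at an analysis by prior BoNT treatment. From what is visible it does not separate former DAXI from former placebo, nor is it tied to immunogenicity.

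**Conclusion.** The point holds in conditional form. On the visible rules, subjects given DAXI in 1720302 have an antibody baseline that follows a DAXI and RTP004 exposure, and their OLS cycle number is one short of their DAXI injection count. Unless redacted text sets a different rule, cumulative incidence since first DAXI is understated, and late-detected conversions are placed in the wrong cycle.

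About 1 to 5 subjects would be reclassified. This assumes that all 350 rollovers enrol, that 50-75% had DAXI, that conversion is 0.5-2% per injection, and that all such conversions are detectable at the OLS baseline. The relative losses in step 3 also assume constant risk per injection. None of the rates or shares comes from the documents.

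Severity is moderate: this is a primary endpoint, but the planned within-OLS table remains interpretable. Confidence is moderate because of the redaction.

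**What to change.** Keep the planned OLS table by dose and cycle. If the redacted SAP text already sets an antibody baseline before the 1720302 injection, a cross-reference from SAP 6.2 settles the baseline question. Otherwise add to the SAP:

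1. For former-DAXI rollovers, treatment-emergent antibody counts (BoNTA and RTP004) against the last sample before the 1720302 injection, where one is available, shown beside the counts against the OLS baseline.
2. Immunogenicity by cumulative number of DAXI injections (1720302 plus OLS), split into former-DAXI rollover, former-placebo rollover and de novo.
3. Where no pre-1720302 sample exists, a supplementary table of DAXI-naive subjects (de novo plus former placebo). It should not replace the main table, because that would drop the former-DAXI rollovers from the main analysis.

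The cost is a merge with the sponsor's 1720302 allocation and antibody data, a few extra tables, and possibly a slightly less favourable reported incidence. The visible text does not confirm that pre-dose antibody samples were taken in 1720302, so this should be checked first.
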